I also have read the current Clinical Investigators’ Brochure for UT-15C (treprostinil diethanolamine) and acknowledge that review of the information contained in the Clinical Investigators’ Brochure is a requirement for investigators before using UT-15C in a clinical trial.

Signature of Principal Investigator

Date

Printed Name of Principal Investigator

PROTOCOL SUMMARY

Protocol Number:	TDE-PH-304
Protocol Title:	An Open-Label Extension Trial of UT-15C SR in Subjects with Pulmonary Arterial Hypertension
Study Phase:	3
Name of Drug:	UT-15C SR (treprostinil diethanolamine)
Indication:	Pulmonary Arterial Hypertension (PAH)
Study Objectives:	
To provide, or continue to provide, UT-15C SR for eligible subjects who participated in protocols TDE-PH-202, TDE-PH-203, TDE-PH-205, TDE-PH-301, TDE-PH-302, TDE-PH-308, or any additional UT-15C SR clinical protocols evaluating subjects with PAH.
 
To assess the long-term safety of UT-15C SR in these subjects through assessment of adverse events and laboratory parameters.
 
To assess the effect of continued therapy with UT-15C SR on exercise capacity after one year of treatment.

Study Design:	This is a multi-center, open-label study for eligible patients who participated in Protocol TDE-PH-202, TDE-PH-203, TDE-PH-205, TDE-PH-301, TDE-PH-302, TDE-PH-308, or any additional UT-15C SR clinical protocols evaluating subjects with PAH.
Sample Size:	Approximately 900 subjects from protocols TDE-PH-202, TDE-PH-203, TDE-PH-205, TDE-PH-301, TDE-PH-302, and TDE-PH-308 plus additional subjects from any additional UT-15C SR clinical protocols evaluating subjects with PAH.
Summary of Subject Eligibility Criteria:	Participation in study TDE-PH-202, TDE-PH-203, TDE-PH-205, TDE-PH-301, TDE-PH-302, TDE-PH-308 or any additional UT-15C SR clinical protocol is required. Subjects must complete all assessments in one of these studies to be eligible.
Drug Dosage and Formulation:	
UT-15C Sustained Release Tablets will be provided as 0.25, 0.5, 1, and 2.5 mg tablet strengths. UT-15C SR tablets may also be provided as a 0.125 mg strength, if available.
 
For subjects on placebo at the end of the TDE-PH-301, TDE-PH-302, and TDE-PH-308 protocols, treatment will be initiated at 0.25 mg twice daily (every 12 hours +/- 1 hour) with dose escalation of an additional 0.25 to 0.5 mg twice daily every 3 days if clinically indicated based upon adverse events and signs and symptoms of PAH. The 0.125 mg strength, if available, may be used throughout the study if a 0.25 mg dose increase is not tolerated and an intermediate dose is required. Doses should be optimized throughout the study. For subjects on active therapy in TDE-PH-202, TDE-PH-203, TDE-PH-205 TDE-PH-301, TDE-PH-302, and TDE-PH-308 the initial dose of the open-label study will be

based upon their ending dose in the previous study, and dose modification will be based on adverse events and signs and symptoms of PAH. Twice daily (BID) dosing should occur (every 12 hours +/- 1 hour) with dose escalation of an additional 0.25 to 0.5 mg twice daily every 3 days if clinically indicated based upon adverse events and signs and symptoms of PAH. Three times (TID) daily dosing for subjects enrolled from the TDE-PH-205 study or those subjects transitioning from BID to TID dosing, study drug should be taken every 6-8 hours with dose escalation of an additional 0.125 to 0.25 mg twice daily every 3 days if clinically indicated based upon adverse events and signs and symptoms of PAH. All study drug should be administered immediately following (~10 minutes) breakfast and dinner for BID dosing and with food for TID dosing.

Route of Administration: Oral

Study Visit Schedule: Study visits will be timed to occur 3, 6, 12, 24, 36 months after each subject's first exposure to UT-15C SR. The study will continue with yearly visits beyond 36 months until either UT-15C SR is approved by the appropriate regulatory authorities or the study is discontinued by the sponsor. Subjects receiving placebo in the previous study (TDE-PH-301, TDE-PH-302, or TDE-PH-308) and subjects enrolled from the TDE-PH-202 study who were in Dose Groups 1 or 2 and permanently discontinued treatment must be contacted weekly by telephone during the first 12 weeks of the open-label study. Subjects transitioning from BID to TID dosing should be contacted weekly for the first four weeks after transitioning. Monthly telephone calls must be conducted for all subjects actively participating in TDE-PH-304, regardless of study drug allocation (UT-15C SR or placebo) in the previous study. In addition to the scheduled study visits, all subjects must be seen in the clinic no less than once every six months for routine standard of care medical evaluation.

Efficacy Assessment: A 6-Minute Walk Test with Borg Dyspnea Score will be conducted at the study visit occurring 1 year after the subject first received UT-15C SR.

Safety Assessments: Adverse events and clinical laboratory parameters will be assessed throughout the study.

Statistical Considerations: All data will be summarized in tables and listings.

Sponsor: United Therapeutics Corporation
[name]
[name]
[name]
United States of America

TABLE OF CONTENTS

LIST OF CONTACTS FOR STUDY	2
INVESTIGATOR AGREEMENT	3
PROTOCOL SUMMARY.....	4
TABLE OF CONTENTS	6
LIST OF ABBREVIATIONS	8
1 BACKGROUND AND RATIONALE.....	9
1.1 Pulmonary Arterial Hypertension: Definition of Clinical Problem	9
1.2 Treprostinil Background	9
1.2.1 UT-15C SR Nonclinical	9
1.2.2 UT-15C SR Clinical Pharmacology	11
1.2.3 Remodulin Experience	13
1.3 Rationale for Development of Study Drug in Disease/Condition.....	13
1.4 Clinical Hypothesis.....	14
2 STUDY OBJECTIVES AND ENDPOINTS	14
2.1 Study Objectives.....	14
2.2 Study Endpoints	14
3 EXPERIMENTAL PLAN	14
3.1 Study Design.....	14
3.2 Overall Schedule of Times and Events	15
3.3 Clinical Assessments.....	16
3.3.1 Efficacy.....	16
3.3.2 Safety	16
3.4 Number of Centers.....	17
3.5 Number of Subjects	17
3.6 Estimated Study Duration	17
4 SUBJECT ELIGIBILITY.....	18
4.1 Subject Inclusion Criteria	18
5 SUBJECT ENROLLMENT	19

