3.2 Overall Schedule of Times and Events

The overall schedule of Time and Events is shown in Table 3.2. Note that the timing of each visit depends upon when the subject first received UT-15C SR (e.g. whether the subject was assigned to active or placebo treatment in Protocol TDE-PH-301, TDE-PH-302, or TDE-PH-308). Subjects receiving placebo in the previous study, or subjects enrolled from the TDE-PH-202 study who are beginning a dose of 0.25mg BID, must be contacted weekly by telephone (at a minimum) during the first 12 weeks of the open-label study to ensure subject safety. More specifically, these calls should assess study drug dose titration needs, potential adverse events, concomitant medication usage and PAH signs and symptoms. Monthly telephone calls (at a minimum) must be conducted for all subjects actively participating in TDE-PH-304, regardless of study drug allocation (UT-15C SR or placebo) in the previous study, to assess dose titration needs, potential adverse events, concomitant medication usage and PAH signs and symptoms. In addition to the scheduled study visits, all subjects must be seen in the clinic no less than once every six months for routine standard of care medical evaluation.

Subjects enrolling from the TDE-PH-203 and TDE-PH-205 studies will transition on the same dose they were receiving at the end of the study. Study visits for the TDE-PH-304 protocol will be based on the date the subject first received active UT-15C in their respective preceding study.

Table 3.2. Time and Events

Assessment	Visit ^{4,5,6,7}						
	Visit 0-1 (Weeks 1-12) ³	1	2	3	4	5+ ⁸	EXIT ⁹
Adverse Events	X	X	X	X	X	X	X
PAH Concomitant Medications	X	X	X	X	X	X	X
Concomitant Medications	X	X	X	X	X	X	X
6-Minute Walk Test/Borg Dyspnea Score ¹				X			
Clinical Laboratory Parameters ²		X	X	X	X	X	X
Drug Accountability/Compliance	X	X	X	X	X	X	X

¹ **6-Minute Walk Test/Borg Dyspnea Score** as described in Appendix A. conducted 3 to 6 hours after the morning dose of UT-15C SR.

² **Laboratories** to be collected are described in Appendix B.

³ **Weekly telephone calls** (at a minimum) required during Weeks 1-12 for subjects randomized to placebo in TDE-PH-301, 302, or 308 to assess dose titration needs, potential adverse events, concomitant medication usage and PAH signs and symptoms. Also applies to subjects enrolled from the TDE-PH-202 study who are beginning a dose of 0.25mg BID.

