⁴ **Visit windows** are ± 1 month from the scheduled number of months from first exposure to UT-15C SR, except for Visit 1, which is ± 2 weeks.

⁵ **VISIT 1** – Only for subjects randomized to placebo in TDE-PH-301, 302, or 308; 3 months after subject's first exposure to UT-15C. Also applies to subjects enrolled from the TDE-PH-202 study who are beginning a dose of 0.25mg BID.

VISIT 2 – 6 months after subject's first exposure to UT-15C SR.

VISIT 3 – 12 months after subject's first exposure to UT-15C SR.

VISIT 4 – 24 months after subject's first exposure to UT-15C SR.

VISIT 5 – 36 months after subject's first exposure to UT-15C SR.

⁶ **Weekly telephone call** required for 4 weeks for all subjects who transition from a BID to TID regimen to assess dose titration needs, potential adverse events, concomitant medication usage and PAH signs and symptoms.

⁷ **Monthly telephone calls** (at a minimum) required for all subjects participating in TDE-PH-304 to assess dose titration needs, potential adverse events, concomitant medication usage and PAH signs and symptoms.

⁸ **Visits beyond Visit 5** will occur yearly until either the drug receives regulatory approval in a particular region or the sponsor discontinues the study. Assessments after visit 5 will include adverse events, PAH concomitant medications, concomitant medications, clinical laboratories, and compliance/drug accountability.

⁹ **EXIT** – If the subject discontinues from the study between scheduled visits, every effort should be made to obtain the exit assessments just prior to termination from the study.

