6.1.3 Three Times (TID) Daily Dosing Regimen

For subjects entering the TDE-PH-304 study receiving a TID dosing regimen (e.g. TDE-PH-205), or for those subjects transitioning from BID to TID dosing, the dosing regimen should be managed as follows:

- TID (every 6-8 hours) with food
- Increases should occur in increments of 0.125 or 0.25 mg TID every 3 days.

In general, the dose of study drug should be increased in 0.125 to 0.25 mg increments every 3 days, in the absence of dose-limiting drug-related side effects, to ensure the subject receives the optimum clinical dose throughout the study. The 0.125 mg strength, if available, may be used throughout the study if a

0.25 mg dose increase is not tolerated and an intermediate dose is required. Dose changes should be conducted under appropriate medical supervision in consultation with the study site.

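### The Protocol Summary and Section 6.1.3 attach different daily frequencies to the same TID escalation increment, and no available text says which prevails

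*Protocol*

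**What the plan says.** The Protocol Summary, under Drug Dosage and Formulation, sets out TID dosing for subjects from TDE-PH-205 and for those moving from BID to TID, and makes escalation conditional on clinical indication. It reads: "study drug should be taken every 6-8 hours with dose escalation of an additional 0.125 to 0.25 mg twice daily every 3 days".

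Section 6.1.3, the section dedicated to the TID regimen, defines its population as follows: "For subjects entering the TDE-PH-304 study receiving a TID dosing regimen (e.g. TDE-PH-205), or for those subjects transitioning from BID to TID dosing". Its bullet on escalation reads "Increases should occur in increments of 0.125 or 0.25 mg TID every 3 days". The paragraph below the bullets repeats the increment with no daily frequency: "In general, the dose of study drug should be increased in 0.125 to 0.25 mg increments every 3 days", subject to tolerability.

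Three other sections bear on the point:

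- Section 6.1 lists tablets of 0.25, 0.5, 1 and 2.5 mg, with a 0.125 mg tablet only if available.
- Section 6.1.2 covers the change from BID to TID and leaves dose modification to the investigator's judgment.
- Section 6.1.4 says that tablets are not to be broken.

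**The concern.** Two current passages of dosing text give different steps for the same subjects. A site that works from the Summary would raise two doses a day, with no indication of which two of the three. A site that works from Section 6.1.3 would raise all three.

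This is neither a difference between current and superseded text nor the effect of a redaction. The BID instructions do not have the problem: the Summary and Section 6.1.1 agree on a BID increment of 0.25 to 0.5 mg every 3 days. The mismatch is confined to TID.

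At stake is consistent escalation across sites for TID subjects. Section 1.4 says the move to TID is meant partly to reduce prostacyclin-related adverse events, so the TID escalation text should be unambiguous.

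**Working it through.** **The two texts side by side**

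| Item | Protocol Summary | Section 6.1.3 |
|---|---|---|
| Subjects | From TDE-PH-205, or moving from BID to TID | Entering on TID (TDE-PH-205 given as an example), or moving from BID to TID |
| Increment | 0.125 to 0.25 mg | 0.125 or 0.25 mg (bullet); 0.125 to 0.25 mg (paragraph) |
| Interval | Every 3 days | Every 3 days |
| Daily frequency of the increment | Twice daily | TID (bullet); none stated (paragraph) |

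The populations match, except that Section 6.1.3 is slightly broader because it names TDE-PH-205 only as an example. The single point of conflict is the last row.

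**Does other text settle it?** Sections 6.1, 6.1.2 and 6.1.4 do not give a TID escalation frequency. Nothing in the available protocol or SAP says that the body prevails over the Summary, or the reverse.

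**Size of one step, read literally**

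Added daily dose = increment × number of daily doses that carry it.

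- Summary: 2 × 0.125 = 0.25 mg/day; 2 × 0.25 = 0.50 mg/day.
- Section 6.1.3: 3 × 0.125 = 0.375 mg/day; 3 × 0.25 = 0.75 mg/day.
- Ratio at the same increment: 0.375/0.25 = 0.75/0.50 = 1.5, so 50% larger under Section 6.1.3.
- Gap per step: 0.375 − 0.25 = 0.125 mg/day; 0.75 − 0.50 = 0.25 mg/day.

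As ranges, the two overlap from 0.375 to 0.50 mg/day. In whole tablets with the same increment on each dose raised, the values are 0.25 or 0.50 mg/day against 0.375 or 0.75 mg/day, and none coincides. They meet only if increments within a day are unequal. For example, 0.125 + 0.25 = 0.375 mg/day under the Summary equals 3 × 0.125 under Section 6.1.3.

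**Without the 0.125 mg tablet**

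The remaining strengths (0.25, 0.5, 1 and 2.5 mg) are all multiples of 0.25 mg, and tablets are not broken. The only increment left within the stated range is 0.25 mg.

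- Summary: 2 × 0.25 = 0.50 mg/day.
- Section 6.1.3: 3 × 0.25 = 0.75 mg/day.

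These do not overlap.

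**Illustration over four weeks**

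Assume that every permitted step is taken for 28 days. That is 9 steps, since 28/3 = 9.3.

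- Summary: 9 × 0.25 = 2.25 to 9 × 0.50 = 4.5 mg/day.
- Section 6.1.3: 9 × 0.375 = 3.375 to 9 × 0.75 = 6.75 mg/day.

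This shows how the gap accumulates if no step is withheld. It does not predict the dose received, because escalation is conditional under both texts.

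The step is not expressed as a percentage of current dose, because the documents do not state the doses that TDE-PH-205 subjects bring into this study.

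**The case against.** The strongest reply is that this is a drafting slip with little consequence. The Summary's *twice daily* may have been carried over from the BID sentence just before it. That same TID sentence requires dosing every 6 to 8 hours, so a careful reader would notice the mismatch and turn to Section 6.1.3. Both texts are guidance: the Summary makes escalation depend on clinical indication, and Section 6.1.3 speaks of what should happen in general.

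There are also safeguards. Section 6.1.3 says "Dose changes should be conducted under appropriate medical supervision in consultation with the study site". Section 3.2 says "Monthly telephone calls (at a minimum) must be conducted for all subjects actively participating in TDE-PH-304", and note 7 to Table 3.2 makes these calls "required for all subjects participating in TDE-PH-304 to assess dose titration needs". Section 3.2 adds that "all subjects must be seen in the clinic no less than once every six months for routine standard of care medical evaluation". Subjects who change from BID to TID also have weekly calls for 4 weeks.

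Most of this stands, and it is why the consequence is called limited. It does not remove the conflict:

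- The documents do not say that the wording is a slip. Unequal doses within a day also occur in this protocol: Table 6-1 has BID examples such as 5 mg in the morning and 5.25 mg in the evening. Its TID examples are all equal, but they illustrate transition doses, not escalation.
- The site that supervises the change is the reader who holds both instructions. Supervision does not tell it which one the protocol intends.
- The four weekly calls apply only to subjects who change from BID to TID. For TDE-PH-205 subjects already on TID, the required minimum is monthly calls, while steps may come every 3 days.

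It is also fair to say that the 50% describes the written step and not a dose received, that the documents do not say how often the 0.125 mg tablet is unavailable, and that they give no evidence that any site was misled.

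**Conclusion.** The concern holds, and the text is wrong as written. For the same TID subjects, the Summary and Section 6.1.3 give steps that differ by a factor of 1.5 at the same increment, a gap of 0.125 to 0.25 mg/day per step. Where only tablets of 0.25 mg and above are available, the written steps have no value in common.

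The figures rest on a literal reading: two doses a day carry the full increment under the Summary, and three under Section 6.1.3. The statement that neither text has precedence applies to the protocol and SAP text available for review.

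This should be fixed because it is a contradiction in current dosing instructions. It is not a threat to the analysis: no effect on the planned SAP summaries is claimed, and existing supervision and contact limit the practical risk.

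**What to change.** Reconcile the TID sentence in the Protocol Summary with Section 6.1.3, so that one escalation instruction with one stated daily frequency appears in both places. State the frequency in the general paragraph of Section 6.1.3 as well. The sponsor's clinical team must choose the instruction; none is proposed here.

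Carry the edit in the next amendment under Section 13.1. That section requires regulatory and IRB/EC approval, and consultation with the investigator if the change counts as altering dosages. Until then, alert sites to the discrepancy and ask them to refer questions to the sponsor, without an interim dosing instruction from this review.

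The cost is small: about one line of text and a short notice to sites. Using the next amendment avoids a separate approval round across approximately 118 centers (Section 3.4) for this item alone.

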	APPENDIX A: Procedure for 6-Minute Walk Exercise Test and Borg Dyspnea Score	
	31	
	APPENDIX B: Clinical Laboratory Parameters	33
	APPENDIX C: Guidelines and Definitions for Recording Adverse Events.....	34
	APPENDIX D: Expected Adverse Events Listing for UT-15C SR Clinical Studies ..	36

LIST OF ABBREVIATIONS

Abbreviation	Definition
AE	Adverse Event
ALT	Alanine Aminotransferase
AST	Aspartate Aminotransferase
BID	Twice Daily
°C	Degrees Celsius
CRF	Case Report Form
EC	Ethics Committee
ERA	Endothelin Receptor Antagonist
FDA	Food and Drug Administration
°F	Degrees Fahrenheit
GCP	Good Clinical Practice
GI	Gastrointestinal
ICH	International Conference on Harmonisation
iMTD	Individual Maximum Tolerated Dose
IRB	Independent/Institutional Review Board
LDH	Lactate Dehydrogenase
MedDRA	Medical Dictionary for Regulatory Activities
mg	Milligram
mL	Milliliter
PAH	Pulmonary Arterial Hypertension
PDE ₅	Phosphodiesterase 5
PGI ₂	Prostacyclin
SAE	Serious Adverse Event
SR	Sustained Release
TID	Three Times Daily
UT-15C SR	Treprostinil Diethanolamine

1 BACKGROUND AND RATIONALE

1.1 Pulmonary Arterial Hypertension: Definition of Clinical Problem

Pulmonary arterial hypertension (PAH), which is defined as an elevation in pulmonary arterial pressure and pulmonary vascular resistance, is a severe hemodynamic abnormality associated with a variety of diseases and syndromes. Elevation in pulmonary arterial pressure causes an increase in right ventricular afterload, impairing right ventricular function and ultimately leading to inactivity and death.

There are three major factors thought to contribute to the increased pulmonary vascular resistance seen in this disease: vasoconstriction, remodeling of the blood vessel wall, and thrombosis. There are a number of metabolic pathways implicated as contributing to these changes including vasoactive mediators such as the vasodilators nitric oxide and prostacyclin, the vasoconstrictor endothelin-1, and the phosphodiesterase type-5 mediated vasodilation. These substances affect not only vascular tone but also effect vascular remodeling and represent current pharmacologic targets.¹

Approved pharmacotherapies for PAH include: (1) intravenous prostacyclin (epoprostenol sodium or Flolan[®])^{2,3}, (2) the prostacyclin analogues, subcutaneous (SC), intravenous (IV), and inhaled treprostinil sodium (Remodulin[®]; Tyvaso[®]) and inhaled iloprost (Ventavis[®]), (3) the oral phosphodiesterase-5 inhibitors (PDE5-I), tadalafil (Adcirca[®]) and sildenafil (Revatio[®]); and (4) the oral endothelin receptor antagonists (ERA)^{9, 10}, bosentan (Tracleer[®]) and ambrisentan (Letairis[®], Volibris[®]).^{11,12}

1.2 Treprostinil Background

1.2.1 UT-15C SR Nonclinical

UT-15C is a novel salt form of Remodulin[®] (treprostinil) Injection and Tyvaso[®] (treprostinil) Inhalation Solution, which are approved in the United States and other countries for the treatment of patients with PAH. The active pharmaceutical ingredient, treprostinil, exists as the sodium salt in the drug product of Remodulin and Tyvaso. Given that the only change to the drug substance synthesis route for UT-15C is the diethanolamine addition step, and treprostinil is not altered, the bioactive form of treprostinil diethanolamine and treprostinil sodium is predicted to be identical. Therefore, in addition to the nonclinical studies conducted with UT-15C, an extensive amount of pharmacology, pharmacokinetic, and toxicology information on treprostinil sodium is available from Remodulin and Tyvaso development. During the development of Remodulin, treprostinil sodium was administered SC and / or IV in acute toxicity studies, repeat-dose toxicity studies, reproductive toxicity studies, and genotoxicity studies, and has a well defined clinical safety profile. Treprostinil sodium was administered via continuous infusion to both rats and dogs in toxicity studies for up to 6-months, which supported the chronic administration of Remodulin to patients.

In addition to the extensive toxicology data with treprostinil sodium, the toxicity and toxicokinetic profiles of UT-15C have been evaluated in acute and repeat dose oral toxicity studies of up to 13 weeks in duration in rodents and up to 9 months duration in dogs. UT-15C has also been evaluated in reproductive-developmental toxicity studies in pregnant rats and rabbits and in an *in vivo* rat micronucleus assay.

Nonclinical findings from 13 week toxicology studies with UT-15C have included dose dependent, yet transient decreases in mean body weight gain and food consumption in both rats and dogs and soft / mucoid stools, diarrhea, and vomitus in dogs. Many of these findings have been seen previously during development of Remodulin and are consistent with prostacyclin induced effects. In addition, post-mortem findings in rats administered UT-15C included changes in organ weight data and histological findings related to the adrenal gland, heart, spleen, thymus and bone marrow; some of which were not seen with Remodulin. The majority of these findings were reversible following a 4-week recovery period. Data from a 9-month dog study provides additional toxicology information following chronic dosing. UT-15C was reasonably well-tolerated following daily oral administration at dose levels up to 35 mg/dog/day for 9 months. The primary adverse effect was judged to be gastrointestinal disturbance, evidenced by increased incidence of soft stools, mucoid stools and diarrhea. By the end of the study, all dogs were in

good condition. No systemic adverse effects were detected as judged by ophthalmology, ECG, clinical pathology and histopathological examination.

In vitro genotoxicity studies with UT-15C have not been conducted; however, data are available for such studies using high doses of Remodulin (treprostinil sodium). Remodulin (treprostinil sodium) was non-mutagenic in bacterial reverse mutation assays (Ames assay) at concentrations up to 5,000 mcg/plate with and without S9 metabolic activation, and in the mouse lymphoma assay at concentrations up to 400 mcg/mL without S9 metabolic activation and up to 300 mcg/mL in the presence of S9. UT-15C was tested *in vivo* in the rat micronucleus assay, which aimed to evaluate the potential of UT-15C to increase the incidence of micronucleated polychromatic erythrocytes in bone marrow of rats. The results of the assay indicated that oral administration of UT-15C at total doses up to and including a dose of 50 mg treprostinil (equivalent to 63.4 mg UT-15C/kg) did not induce a significant increase in the incidence of micronucleated polychromatic erythrocytes in either male or female SD rats. Mortality observed at the high dose indicates systemic exposure of animals to the test article. Based upon these findings, treprostinil diethanolamine (UT-15C) was concluded to be negative in the rat micronucleus assay.

Segment I (rat) and Segment II (rat and rabbit) reproductive and developmental toxicology studies have also been conducted. No adverse effects for fetal viability / growth and fetal development (teratogenicity) were seen in rats at or below 20 mg/kg/day or rabbits at or below 0.5 mg/kg/day. At high doses, there were teratogenic effects of UT-15C observed when administered to rabbits. Findings included increased fetal incidence of external, soft tissue, and skeletal malformations. Additionally, a Segment III reproductive and developmental toxicology study has been conducted in female rats. F0 female rats receiving 10 mg/kg/day had decreased food consumption and body weights during gestation, increased duration of gestation, had slight decreases in the viability and number of pups per litter, and pups with decreased mean neonatal body weights. F1 pups of females that received 20 mg/kg/day had abnormalities in physical development (developmental landmarks), reflex development, exploratory behavior, learning and memory, and sexual maturation.

A six month carcinogenicity study in hemizygous Tg.rasH2 mice administered UT-15C at daily oral doses of 3, 7.5, 15 mg/kg and 5, 10, 20 mg/kg in females and males, respectively, for 26-weeks did not increase the incidence of neoplastic lesions. A two year rat carcinogenicity study is ongoing.

Studies have been conducted by the United States National Toxicology Program (NTP) to determine whether diethanolamine by itself (without treprostinil or any other drug) causes cancer. Two years of topical administration of diethanolamine to mice produced an increased incidence (compared to a control group) of malignant liver tumors in males and females, as well as an increased incidence of malignant kidney tumors in males. Doses used in this study were approximately 720 to 2,900 times higher (based on mg/m² dosing) than the proposed starting doses for the UT-15C clinical studies. However, in transgenic mice and rats, topical administration of diethanolamine for twenty weeks and two years, respectively, was not associated with the development of any cancers. The relevance of the mouse tumor findings to humans is currently unknown. Diethanolamine is listed on the FDA database of inactive ingredients for a number of approved drug products with no apparent safety concerns.

A GLP cardiovascular safety pharmacology study (Study 1259DU16.003) to evaluate diethanolamine effects, independent of treprostinil, on cardiovascular function in telemetered dogs has been conducted. Since there are 0.269 grams of diethanolamine per each gram of treprostinil in UT-15C, for this study, doses of diethanolamine were selected that were similar or higher than the amount of diethanolamine contained in the doses of UT-15C assessed in the UT-15C cardiovascular safety pharmacology study (Study 1259DU16.002). Doses of 0, 2, 3 and 4 mg/kg/day of diethanolamine (equivalent to the amount of diethanolamine administered with 7, 11, and 15 mg/kg/day of treprostinil, the free acid of UT-15C), were selected to be administered to each of one group of four telemetered male dogs. Oral administration of diethanolamine at doses up to 2 mg/kg/dose twice daily (4 mg/kg/day) to male beagle dogs was not associated with any definitive changes in arterial pressure, heart rate or electrocardiogram parameters. In addition, no abnormal clinical signs were noted in the animals dosed with the vehicle or with any of the doses of diethanolamine.

